cardiopulmonary bypass strategy based on blood gases and operative documents.

Inclusion Criteria:

• Age less than 30 days of age at time of surgery with need for cardiopulmonary bypass with

cardioplegic arrest (with or without deep hypothermic circulatory arrest)

• Diagnosis with cyanosis at baseline (pre-operative PaO2 of less than 50mmHG) due to:

o Complete admixture lesion (example: hypoplastic left heart syndrome, total anomalous

pulmonary venous return, truncus arteriosus, pulmonary atresia with VSD)

o Transposition physiology (example: D-Transposition of the great arteries or Double

outlet right ventricle with subpulmonary VSD)

o Right-to-left shunt (example: Tetralogy of Fallot, double outlet right ventricle with

suboaortic VSD and pulmonary stenosis)

Exclusion Criteria:

• Corrected gestation at time of surgery less than 37 weeks

• Prior cardiac arrest

• Current or prior history of ECMO support

• Current or prior history of needing renal replacement therapy with dialysis

• Prior cardiac surgery requiring cardiopulmonary bypass

• Diagnosis of Ebstein's Anomaly

• Known genetic syndrome other than Trisomy 21 or DiGeorge Syndrome

ProtocolVersion: 1.4 Date: 03122021

7

Subject Availability:

Based on historical data, the number of patients that fit the inclusion criteria would be about 40-50 patients

per year in this single center study. A sample size of 21 patients per treatment group (42 total patients) will

be enrolled. With a 50-67% consent rate, the study duration will be approximately 24 months.

Trial Enrollment and Randomization:

Infants will be randomized into two groups:

1. Normoxia Group (with controlled re-oxygenation):

a. Goal PaO2 on cardiopulmonary bypass of 60-100 mm Hg using lower FiO2 (blended

sweep gas) via oxygenator

b. Post-bypass, goal of PaO2 < 100 mm Hg by anesthesia and in ICU via oxygen titration via

mechanical ventilator for 24 hours post-op.

2. Standard of Care Group: Current standard of care

Randomization will be performed in random permuted block sizes of 2 or 4 and stratified by "Stage I

Palliation" (Norwood arch reconstruction with shunt placement [Right ventricle-to-pulmonary artery shunt,

modified Blalock-Taussig shunt, or central aortopulmonary shunt]) in each treatment group. Patients

undergoing Stage I palliation are known to have higher rates of complications and mortality at baseline and

therefore the stratification will be done to control for this in the randomization.

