Specific Aim 1: The primary outcome for this aim will be systemic oxidative stress based on thiobarbituric acid reactive substances (TBARS), a measurement of lipid peroxidation, assessed at three separate time points in the first 24 hours after surgery. An analysis of co-variance will be used incorporating all available data to model the outcome with an adjustment for pre-operative baseline (although we anticipate no differences in baseline values by treatment arm due to randomization). The model will compare the mean values (and 95% confidence intervals) between the two groups at each time-point. In this model, we will assume missing data are missing at random, i.e., missing values may depend on observed but not unobserved data. Analysis will be performed on the basis of the intent-to-treat principle and will include an interim analysis after 24 patients are enrolled. In secondary analyses, we will use propensity scores to

account for any characteristics that were not balanced by treatment arm after randomization. We plan to

analyze other biomarkers of oxidative stress and organ injury using analogous analysis of variance models.

Specific Aim 2: To evaluate safety, we will assess the rate of observed adverse events between groups using

Chi-square test or Fisher's exact test as appropriate. Safety will also closely be monitored on a routine basis

by the Data Safety and Monitoring Board (DSMB). .

Specific Aim 3: To investigate optimal endpoints in the study of the clinical impact of normoxia. We will

assess clinical endpoints that may be reflective of a reduction in oxidative stress, including post-operative

length of stay, days alive and out of the intensive care unit (ICU) at 30 days after surgery, a composite

outcome of major adverse events as described above, and a global rank score. For all endpoints, data on

distribution within our study population and between the two groups will be calculated to understand effect

sizes and aid in planning subsequent studies.

1. Post-operative length of stay: Calculated as number of days in the hospital after surgery. May be an

attractive outcome as it can incorporate many of the morbidities that would be influenced by strategies to

reduce oxidative stress as most would lead to prolonged length of stay. The disadvantages are that it does

not incorporate mortality, and may be influenced by other center care processes and practices.

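### Randomisation is stratified by Stage I palliation, but no analysis model includes the stratum; if Stage I predicts TBARS beyond baseline, the confidence intervals for the arm difference are too wide and power is lost

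*Combined protocol and SAP*

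**What the plan says.** Under Trial Enrollment and Randomization: "Randomization will be performed in random permuted block sizes of 2 or 4 and stratified by" Stage I palliation. The reason given is that these infants start with a greater risk of complications and death, and the section concludes: "therefore the stratification will be done to control for this in the randomization". Subject Availability fixes the size: "A sample size of 21 patients per treatment group (42 total patients) will" be enrolled.

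Under Outcomes and Analysis, Specific Aim 1, the primary model for TBARS is: "An analysis of co-variance will be used incorporating all available data to model the outcome with an adjustment for pre-operative baseline". The output is described as: "The model will compare the mean values (and 95% confidence intervals) between the two groups at each time-point". For the remaining markers the plan is to "analyze other biomarkers of oxidative stress and organ injury using analogous analysis of variance models", with no covariate named. A secondary propensity-score analysis is meant to "account for any characteristics that were not balanced by treatment arm after randomization".

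Stage I appears in the randomisation scheme and in no analysis model.

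**The concern.** Stratified permuted blocks make the arms nearly equal in their number of Stage I infants, so any Stage I effect on TBARS largely cancels out of the arm difference. The true sampling error of that difference is therefore close to the within-stratum error. A model without the stratum estimates its residual variance from all infants pooled and includes the gap between strata. If Stage I predicts post-operative TBARS beyond baseline TBARS, the reported standard error exceeds the true one, intervals over-cover, and the test rejects too rarely.

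The propensity-score analysis does not close the gap. It is secondary, and it is triggered by characteristics found unbalanced, which a stratification factor will normally not be.

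What is at stake is precision in a 42-infant pilot whose third aim is to estimate effect sizes for later trials.

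**Working it through.** **Inputs from the documents.** 42 infants, 21 per arm; blocks of 2 or 4 within Stage I strata; ANCOVA on arm and baseline; 95% CIs.

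**Inputs not in the documents (assumed).** Stage I share 30% or 50%; two-sided 5% level; no missing data; one time point; the TBARS effects given below.

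**The plan's own figure.** The sample size of 42 cannot be reproduced, because no alpha, power, effect size or SD is given. Working backwards, 21 per arm gives 80% power for a difference of 0.886 SD by two-sided t-test.

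**Step 1: balance.** In 20,000 simulated allocations per share, the arms differed by at most 2 Stage I infants, and by 0 or 1 in about 94% of trials.

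**Step 2: CI width by formula.** Let the within-stratum outcome SD be 1 and the baseline correlation 0.4, so the residual variance with Stage I in the model is 1 − 0.4² = 0.84. Let q = share × (1 − share), which is 0.21 or 0.25, and let d be the Stage I shift in outcome. If baseline TBARS is unrelated to Stage I, the share of post-baseline variance explained by Stage I is R² = q d² / (0.84 + q d²). The width ratio, baseline-only to adjusted, is 0.999 / √(1 − R²), where 0.999 is the ratio of the t quantiles on 39 and 38 degrees of freedom.

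| Shift d | Share | R² | Width ratio |
|---|---|---|---|
| 0.5 | 30% | 0.0525/0.8925 = 0.059 | 1.030 |
| 0.5 | 50% | 0.0625/0.9025 = 0.069 | 1.036 |
| 1.0 | 30% | 0.21/1.05 = 0.200 | 1.117 |
| 1.0 | 50% | 0.25/1.09 = 0.229 | 1.138 |
| 1.5 | 30% | 0.4725/1.3125 = 0.360 | 1.249 |
| 1.5 | 50% | 0.5625/1.4025 = 0.401 | 1.291 |

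If baseline also shifts, by a, it carries part of the Stage I difference. The residual variance without Stage I is then 1 + q d² − (0.4 + q a d)² / (1 + q a²). For d = 1 and q = 0.21:
- a = 0.5: 1.21 − 0.505²/1.0525 = 0.968, ratio 0.999 × √(0.968/0.84) = 1.07.
- a = 1: 1.21 − 0.61²/1.21 = 0.9025, ratio 0.999 × √(0.9025/0.84) = 1.04.

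**Step 3: simulation.** 8,000 trials per scenario, true effect 0.8 within-stratum SD. Power with the stratum included is 77-79% throughout. Entries are CI widening / power of the baseline-only model.

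| Shift d | Baseline unrelated | Baseline shifts half as much | Baseline shifts equally |
|---|---|---|---|
| 0 | 0% / 78% | | |
| 0.5 | 3-4% / 76% | 2% / 76-77% | 1% / 77% |
| 1.0 | 12-14% / 68-70% | 7-9% / 72-73% | 3-4% / 75-76% |
| 1.5 | 25-30% / 57-60% | 15-18% / 66-67% | 6-7% / 73% |

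Bias is within 0.005 SD in both models. Type I error without the stratum runs from 1.3% to about 5%.

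**Step 4: second simulation, scaled differently.** The total post-baseline variance is held fixed and Stage I explains a share R² of it. The effect is 0.886 SD, with 10,000 trials per setting; the 30% share is shown.

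| R² | CI widening | Coverage, baseline-only | Type I, baseline-only | Power, baseline-only | Power, adjusted |
|---|---|---|---|---|---|
| 0 | none | 95.1% | 4.9% | 78.7% | 78.3% |
| 0.05 | 2.5% | 95.6% | 4.4% | 79.5% | 81.0% |
| 0.10 | 5.4% | 95.8% | 4.2% | 79.6% | 82.6% |
| 0.20 | 11.9% | 97.1% | 2.9% | 81.7% | 87.2% |
| 0.30 | 19.8% | 98.0% | 2.0% | 82.3% | 90.8% |
| 0.40 | 29.5% | 98.6% | 1.4% | 83.7% | 94.3% |

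The mechanism shows in the standard errors. At R² = 0.20 the baseline-only model reports 0.312 on average against an empirical 0.280; at R² = 0.40, 0.312 against 0.251. The adjusted model stays near 95% coverage throughout.

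**The case against.** - **The condition is unproven.** The protocol calls Stage I prognostic for complications and mortality, not for TBARS, and gives no TBARS SD or Stage I share. This stands, and it is why the loss is a range from zero. A link is plausible: the Background lists diagnosis and type of procedure among likely contributors to organ injury, and several of the other biomarkers measure such injury. The section on weaning from bypass also sets different oxygen goals by ventricular physiology, and these are kept for 24 hours.
- **The large figures are one corner of the grid.** True. Widening of 25-30% needs Stage I to explain about 36-40% of the variance left after baseline. At R² of 0.10 or less the CI is at most about 5% wider, and about 3 points of power are lost.
- **The fall in power depends on scaling.** Also true. Step 3 adds Stage I variance to a fixed within-stratum SD, so baseline-only power drops. Step 4 fixes the total, so the same omission appears as a gain not taken. The gap between models is real either way, and the plan states no power target to fall short of.
- **The error is conservative, in a pilot.** Correct. This is an efficiency point, not a threat to validity.
- **The checks simplify the plan.** They use one time point, while the plan has three and allows for missing data. If the Stage I effect varies over time, a single common term may not recover all the precision. The over-coverage shown is for the arm difference, not for intervals around each group mean, which the plan's wording could also mean. Neither point argues for leaving the stratum out.

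**Conclusion.** The concern holds. The primary ANCOVA names baseline alone, the other biomarker models name no covariate, and the stratification factor is in none of them. If Stage I predicts TBARS beyond baseline, CIs for the arm difference are too wide and power is lost. If it does not, nothing is lost. Across the assumed scenarios the widening runs from 0% to 30%, and the size cannot be narrowed from the documents. It is small where baseline TBARS already carries most of the Stage I difference. The estimate stays unbiased and false positives do not rise materially above 5%. The change is worth making because the possible gain is appreciable and the cost close to nil.

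**What to change.** In Specific Aim 1, pre-specify Stage I palliation (yes/no) as a fixed covariate alongside baseline in the primary TBARS ANCOVA, and state the same for the analogous biomarker models. If one model spans the three time points, say whether the Stage I term is common to them or specific to each.

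The cost is one line of text and, for a single term, one degree of freedom. The factor is known for every infant at randomisation. If Stage I is not prognostic, the CI widens by 0.1-0.2% at 42 infants and by 0.3-0.6% at the 24-patient interim analysis, with power essentially unchanged. Two further benefits follow. Naming the covariate now rules out a data-driven choice later. If missing samples are related to Stage I, having it in the model also makes the missing-at-random assumption easier to defend.

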Ihnken et al	nken et al 1998 Adult (mean 40 Randomized to hypero 61 years) CPB (PaO2 400) vs normoxia (PaO2 140)			No adverse events reported	Statistically significant increase in oxidative stress biomarkers and myocardial damage in hyperoxic group compared to normoxia. No differences in clinical outcomes of ICU/hospital stay. Statistically significant decrease in lung function measured by PFTs in hyperoxia group 5 days post-operatively			

Overall, pediatric clinical and pre-clinical experimental studies suggest that there is a likely benefit

to normoxic and controlled re-oxygenation during cardiac surgery. However, there are several limitations

to the published data including single center studies enrolling a wide age range, heterogeneous patient

populations encompassing a wide variety of cardiac diagnoses and surgical procedures, and an inconsistent

approach to preventing early exposure to supra-physiologic oxygen levels. Furthermore, results from an

informal survey of other large pediatric cardiac surgery centers (Table 2) and survey data from 39 centers

from a large multi-institutional registry (NPC-QIC) (Figure 1) indicates that most centers utilize a supra-

physiologic oxygen management strategy and that there is significant practice variation with regards to goal

oxygen levels during cardiopulmonary bypass. Therefore, the goal of this proposed study is to investigate

the use of normoxia or near-physiologic oxygen levels before, during, and after cardiopulmonary bypass in

a well-defined, high-risk cyanotic neonatal population undergoing a select number of surgeries. The study

will be a pilot single center study to show efficacy and safety with the eventual goal of a larger multi-center

study that will be powered to show a true difference in clinical outcomes.

Table 2: Survey results from large pediatric cardiac surgery centers reporting PaO2 management on bypass practice.

PHN Center	Practice with regards to PaO2 management on Bypass				
Michigan	All patients: 200-300				
MUSC	Cyanotic patients at baseline: Initiate at 70-100 and 150 during rewarming.				
	All other patients: 150-250				
Emory	All patients: 250-300				
Boston Children's	All patients: >500				
СНОР	All patients: 200-250				
Texas Children's	All patients: Goal 150-250				
Sick Kids Toronto	All patients: Goal 120-150 on bypass				
	Cyanotic patients: Initiate bypass with PaO2<100 and then increase to goal				

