Cincinnati Children's	Cyanotic patients at baseline: Initiate bypass at 21% FiO2 and then increase to 200-250. Decrease to 80-120 prior to cross clamp removal and then goal of 200-250				
	All other patients: Maintain >200, decrease to 80-120 just prior to cross clamp removal and then 200-250 afterwards				

ANSWER CHOICES	RESPONSES
Match patient's baseline	0.00%
< 30	0.00% 0
30 - 70	0.00% 0
71 - 120	15.38% 6
121 - 200	30.77% 12
201 - 300	43.59% 17
301 - 400	2.56% 1
> 400	7.69% 3
TOTAL	39

Figure 1: Survey Data results of NPC-QIC Perfusion Practices: Goal PaO2 while on cardiopulmonary bypass.

Specific Aims:

To assess oxidative stress and end organ injury in the normoxia versus supra-physiologic oxygen groups.
 Hypothesis 1a: Normoxia will be associated with reduced oxidative stress as measured by
 thiobarbituric acid reactive substances (TBARS), a marker of lipid peroxidation. We also anticipate
 reductions in other measures including protein carbonyl, 8-isoprostane, and whole blood reduction oxidation potential.

Hypothesis 1b: End organ injury will be reduced as assessed by biomarkers of renal (Neutrophil gelatinase-associated lipocalin), neurologic (Glial fibrillary acidic protein, Tau), liver (Intestinal fatty-acid binding protein), vascular (Angiopoietin 2), and myocardial injury (Troponin I) as well as immune system activation (IL-6, IL-10).

- To evaluate the safety profile of a strategy of normoxia versus supra-physiologic oxygen.
 Hypothesis: Observed major adverse events including in-hospital mortality, cardiac arrest, need for mechanical circulatory support, seizures, and dialysis will be similar or lower in the normoxia group.
- 3. To investigate optimal endpoints in the study of the clinical impact of normoxia.

We will assess clinical endpoints that may be reflective of a reduction in oxidative stress to understand effect sizes and inform the design of subsequent trials. These endpoints will include post-operative length of stay, days alive and out of the intensive care unit (ICU) at 30 days after surgery, a composite

outcome of major adverse events as described above, and a global rank score.

Study Design:

Participants:

Single center (University of Michigan) randomized pilot study in infants less than 30 days of age

undergoing heart surgery with cardiopulmonary bypass. The trial will be unblinded with respect to

knowledge of treatment assignment as the majority of clinical personnel will have knowledge of the

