B). "Unexpected". An event is considered unexpected if there are no prior data linking this
event with either the condition or intervention under study.
In terms of relation to the intervention, the Serious Adverse Event will be classified as:
a) definitely related to the intervention
b) probably related to the intervention
c) possibly related to the intervention
d) unlikely to be related to the intervention
e) definitely not related to the intervention

The clinical outcome of the Serious Adverse Event will be characterized as follows:

(a) Death

(b) Recovered: the patient returned to baseline status

(c) Symptoms continue

Data Safety Monitoring Board (DSMB)

A Data and Safety Monitoring Board will be established. The DSMB will meet 4 times a year to review

study conduct, adverse events, and any interim data.

After each DSMB meeting, a Summary Report of Adverse Events will be prepared within 30 days and will

be distributed to the Principal Investigator with instructions that the Principal Investigator forward the

Summary Report to the IRB. The Summary Report will contain the following information:

A statement that a DSMB review of outcome data, adverse events, and information relating to study

performance took place on a given date

A statement as to whether or not the frequency of adverse events exceeded what was expected and

indicated in the informed consent

A statement that a review of recent literature relevant to the research took place

The DSMB's recommendation with respect to progress or need for modification of the protocol or

informed consent. If the DSMB recommends changes to the protocols or informed consent, the

rationale for such changes and any relevant data will be provided

Reporting of Adverse Events/Serious Adverse Events

Reports of Adverse Events/Serious Adverse Events will be submitted to the local Institutional Review

Board (IRB) per institutional guidelines. The PI will report any serious adverse event to the DSMB Chair

20

as soon as possible and no later than 7 calendar days after the event.

All events/complications and all events reported as serious adverse events will be tabulated and reviewed

by the DSMB at their regularly-scheduled meetings, at least 4 times per year.

Data Collection Procedures for Adverse Events/Serious Adverse Events

1. The five events specified as Serious Adverse Events are to be reported in an expedited fashion. Any

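### Does the interim analysis after 24 of 42 infants, planned without a stated boundary, inflate the type I error for TBARS?

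*Combined protocol and SAP*

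**What the plan says.** The interim look appears once, in the Specific Aim 1 paragraph of Outcomes and Analysis: "Analysis will be performed on the basis of the intent-to-treat principle and will include an interim analysis after 24 patients are enrolled". The same paragraph makes TBARS at three post-operative times the primary outcome, analysed by baseline-adjusted analysis of covariance. The only inference it describes is this: "The model will compare the mean values (and 95% confidence intervals) between the two groups at each time-point". Subject Availability fixes enrolment at 21 per group, 42 in total. No significance level, power or sidedness is stated anywhere.

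Under Data Safety Monitoring Board, the board meets quarterly and is given "study conduct, adverse events, and any interim data". After each meeting a Summary Report of Adverse Events is prepared. Its listed contents include a line that opens "A statement that a DSMB review of outcome data, adverse events, and information relating to study", a statement on whether adverse events were more frequent than expected, and the board's "recommendation with respect to progress or need for modification of the protocol" (the consent form is covered as well).

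On purpose, the Background describes a "pilot single center study to show efficacy and safety with the eventual goal of a larger multi-center" trial to follow. Only that later trial is called a "study that will be powered to show a true difference in clinical outcomes". Hypothesis 1a is directional, with TBARS as the marker: "Normoxia will be associated with reduced oxidative stress as measured by" that marker.

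**The concern.** A planned interim analysis normally comes with an outcome, a purpose, a list of who sees results by arm, and a rule linking results to action. None of these is given. Because the sentence sits between the TBARS model and its secondary analyses, a reader will take TBARS as the target, and ordinary 95% intervals are the only inference in view. The DSMB may see interim data and comment on progress, and the Background speaks of showing efficacy.

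Put together, this could be read as two unadjusted looks at the primary outcome. If a nominal 5% result at 24 infants could stop the trial or support a TBARS claim, false positives would rise. An early positive would also overstate the effect carried into the larger trial.

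**Working it through.** **Inputs.** From the documents: interim after 24 infants (Specific Aim 1); final sample 42, equal arms (Subject Availability). Assumed: TBARS is the target; two-sided 5% per comparison, inferred from the 95% intervals; for the exaggeration figures, 80% power at 42. The documents give no error rate or power to reproduce.

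**Case A: the plan as written.** Enrolment runs to 42 and the groups are compared once at the end. With no efficacy decision attached to the look, the error for one comparison is P(|Z2| > 1.96) = 5.0%. The look adds nothing.

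**Case B: a nominal 5% result at either look is acted on.**

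1. Information fraction: 24/42 = 0.571. Correlation between the interim and final statistics: √0.571 = 0.756.
2. Overall error: P(|Z1| > 1.96 or |Z2| > 1.96) = 0.05 + 0.05 − P(both). The bivariate normal with correlation 0.756 gives P(both) = 0.0194, so the total is 0.0806, or 8.1%.
3. Small-sample checks: simulated t-tests with 12 then 21 per arm give 8.1%; simulated analysis of covariance, with an assumed baseline-outcome correlation of 0.5, gives 8.2%. If only 20 of the 24 infants have samples at the look, the normal calculation gives 8.4%.
4. Benefit direction only, which is what Hypothesis 1a concerns: P(Z1 > 1.96 or Z2 > 1.96) = 4.0%, against 2.5% with no look, a rise of 1.5 points.
5. Exaggeration. The drift at 42 is 1.96 + 0.84 = 2.80; at 24 it is 2.80 × 0.756 = 2.12. The mean estimate given a significant result, relative to the truth, is 1 + φ(1.96 − θ)/(θ × P(Z > 1.96)), where θ is the drift.
   - Interim: 1 + 0.394/(2.12 × 0.563) = 1.33.
   - Final analysis with no look: 1 + 0.280/(2.80 × 0.80) = 1.12.

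   An early positive would therefore average 1.33 times the truth, but a significant final result with no interim already averages about 1.12.

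**Case C: a strict guard.** Requiring p < 0.001 at 24 and 0.05 at 42 gives 5.01%. That controls the error in Case B. Against Case A it gains nothing, because there is no early decision to guard.

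**Which case the documents support.** Case B needs three things that no section states: TBARS as the target of the look, a 5% level, and a rule allowing action on a nominal interim result. The DSMB wording does not supply the third. The phrases about outcome data and progress are listed contents of an adverse event report that goes to the investigator and then the IRB. Within Outcomes and Analysis, the DSMB is mentioned only under Specific Aim 2, which is safety. The documents support Case A.

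**The case for a change.** The strongest reply is that an efficacy use is not excluded either. Safety has its own paragraph, yet the interim sentence sits with TBARS. The DSMB may see any interim data, the Background says the pilot is meant to show efficacy, and a rule chosen after arm-level results are seen cannot protect a claim. Stating a rule would cost a few sentences and almost no power.

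Part of this stands. The purpose of the look is unwritten, and the sensible time to record it is before results by arm are seen. But the step from unwritten to inflated requires a decision that the plan does not provide for. Recording that the look concerns conduct, safety or variance would describe the plan as it already reads, without altering it.

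A related argument is that a boundary needs one named TBARS contrast, since three times are compared. That multiplicity exists with or without the interim. Resolving it is a scientific trade-off: for an effect with 80% power at a single time, an overall mean across the three times has 83% to 93% power if the effect is equal throughout, but 16% to 21% if it appears at one time only (between-time correlation 0.9 to 0.5, assumed). The plan's choice to estimate at each time is defensible for a pilot.

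**Conclusion.** The omission is real and the 8.1% is arithmetically correct, but it belongs to a design the documents do not describe. With enrolment to 42 and no efficacy stop, the look leaves the error at the nominal level for one comparison, 5% if the 95% intervals are taken to imply it. Only if a nominal interim result were acted on would it reach about 8.1% two-sided, or 4.0% against 2.5% in the benefit direction. Even then the effect would be confined to a biomarker claim in a pilot and to what is carried into the next trial. This is a missing detail that competent analysts and a DSMB fill sensibly. No change to the plan is needed.

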lactate measurements will be used to verify appropriate oxygen delivery.

"Standard of Care" Group: As cardiopulmonary bypass is being weaned, anesthesia will initiate mechanical

ventilation per standard protocols. Ventilation will be continued in the ICU and adjusted per standard goals

per the intensivist.

5. Post-Operative Course:

After transfer to the PCTU from the OR, the goals as stated above based on the patient's physiology will

be maintained for 24 hours after the surgery per the goals per group and physiology.

After cardiac surgery, the following tests and evaluation will be performed:

1. At 2, 6, and 24 hours after surgery (time marked as decannulation from cardiopulmonary

biomarkers for oxidative stress, inflammation, vascular injury, neurologic,

myocardial, and renal injury will be drawn.

2. At 24, 48, and 72 hours after surgery: renal function and liver function panels will be obtained

3. A head ultrasound will be performed at 24 and 72 hours after surgery

4. EEG monitoring may be connected to each infant after arrival to the ICU as part of the standard

of care.

6. Adverse Event Assessment

Assessment of Serious Adverse Events will be performed 1month post surgery. A chart review will be

performed by the study team. If a chart review can't be accomplished, the study team will contact the patient

[figure not shown]
via phone call for an assessment. See Serious Adverse Event section of the protocol for specific definitions.

10

Date: 03122021

ProtocolVersion: 1.4

Figure 2: Study protocol flow chart

Outcomes and Analysis:

Analysis will be performed on the basis of the intent-to-treat principle. Baseline characteristics will be compared between the treatment groups using standard univariate tests.

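### The secondary TBARS analysis picks its propensity-score covariates by chance imbalance after the data are seen; at 21 per arm this can cost precision and gives miscalibrated intervals

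*Combined protocol and SAP*

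**What the plan says.** The opening of Outcomes and Analysis states: "Baseline characteristics will be compared between the treatment groups using standard univariate tests". It names no characteristics and no threshold.

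Under Specific Aim 1 the primary model is described as follows: "An analysis of co-variance will be used incorporating all available data to model the outcome with an adjustment for pre-operative baseline". The same paragraph then adds a secondary propensity-score analysis, with this stated purpose: "account for any characteristics that were not balanced by treatment arm after randomization". It does not say whether the score is used for matching, weighting, stratification or as a covariate, what counts as unbalanced, or which characteristics are candidates.

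Trial Enrollment and Randomization specifies two groups allocated in permuted blocks of 2 or 4, stratified by Stage I palliation. The reason given is prognostic, namely that these infants have more complications and deaths: "therefore the stratification will be done to control for this in the randomization". No outcome model names this stratum. Subject Availability sets the size at 21 per group, 42 in total.

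**The concern.** In a randomized trial any difference in pre-randomization characteristics is due to chance. Choosing adjustment variables because they happen to differ tells us nothing about whether they predict TBARS, and prognostic value is what makes adjustment useful. The model cannot be written down until the unblinded baseline table exists, and the wording allows many versions of it from the same data.

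This is the only adjusted analysis stated beyond baseline TBARS. The study is a pilot meant to inform a larger trial, so an adjusted estimate with an unreliable interval would be a poor guide. Meanwhile the one factor that the protocol itself calls prognostic, Stage I palliation, is left out of the stated models.

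**Working it through.** **Inputs from the protocol.** 21 per arm, stratified permuted blocks, and a primary ANCOVA adjusted for baseline. Two-sided 5% testing is assumed from the 95% confidence intervals. The protocol gives no effect size, SD, power or prognostic strengths, so there is no stated figure to reproduce and everything about prognosis below is an assumption.

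**How often chance imbalance appears.** For a continuous covariate:

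- SD of the standardized difference = sqrt(2/21) = 0.309.
- Smallest difference significant at 5% = t(0.975, 40) × 0.309 = 2.021 × 0.309 = 0.62 SD.
- P(|difference| > 0.25 SD) = 2 × [1 − Φ(0.25/0.309)] = 42%.
- P(|difference| > 0.10 SD) = 2 × [1 − Φ(0.10/0.309)] = 75%.
- P(at least one of k independent covariates has p < 0.05) = 1 − 0.95^k, which is 40% for k = 10, 54% for k = 15 and 64% for k = 20.

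A significance screen with 10 candidates selects nothing in about 60% of trials. A 0.10 SD cut-off selects most of them. The protocol leaves that choice open.

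**What the step does to the estimate.** Simulation of 42 infants with no treatment effect, 2,500 trials in each of 24 scenarios. Assumed inputs: baseline-outcome correlation 0.5; 40% Stage I with a 0.5 SD effect; 10 or 15 candidate covariates jointly explaining 0, 10, 30 or 50% of outcome variance; unbalanced defined by p < 0.05, p < 0.10, or a difference above 0.25 or 0.10 SD (only p < 0.05 and 0.25 SD with 15 covariates); the score used as a covariate or as inverse-probability weights.

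True SD of the treatment estimate, as a ratio to baseline-only ANCOVA, over all scenarios:

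| Variance explained | Score as covariate | Weighting |
|---|---|---|
| 0% | 1.03-1.21 | 1.05-1.26 |
| 10% | 1.02-1.16 | 1.03-1.22 |
| 30% | 0.93-1.06 | 0.99-1.12 |
| 50% | 0.76-0.98 | 0.86-1.00 |

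**What the reported interval shows.** The average reported SE was about 2.5-14% larger than for baseline-only ANCOVA in every scenario where it could be computed, including those where the true SD fell. Type I error ranged from 0.1% to 4.7% with the score as covariate and from 1.0% to 7.6% with weighting.

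The weighting results with 15 candidates and the 0.25 SD rule (about 6.3 selected on average) show the mechanism:

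| Variance explained | True SD | Reported SE | Baseline-only reported SE | Type I error |
|---|---|---|---|---|
| 0% | 0.348 | 0.308 | 0.281 | 7.6% |
| 10% | 0.329 | 0.309 | 0.281 | 6.1% |
| 30% | 0.299 | 0.310 | 0.280 | 3.8% |
| 50% | 0.265 | 0.308 | 0.280 | 2.2% |

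The reported SE stays near 0.31 whatever the truth. It is too small at 0% (0.308/0.348 = 0.89) and too large at 50% (0.308/0.265 = 1.16).

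**Second simulation, also with 42 infants and assumed inputs.** Reported SEs were 0.285-0.316 against about 0.28 for baseline-only ANCOVA (ratios 1.02 to 1.13). Type I error was 0.9-6.0%. Power was 70-82%, against 81-84% for ANCOVA on baseline and Stage I. At 50% of variance explained the true SD fell to 0.22 against 0.28.

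**The replacement.** In the 24 scenarios, ANCOVA on baseline TBARS plus the Stage I stratum left the true SD unchanged (ratio 0.99-1.00), because the blocks already balance that factor. Its reported SE was 0.268-0.270 against 0.278-0.281 (0.270/0.281 = 0.96, about 4% smaller), with type I error 4.2-5.9%. Two further pre-specified covariates changed the true SD by a factor of 0.94-1.03, with gains only when they were prognostic.

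**The case against.** The strongest reply is that adjusting for chance imbalance is legitimate and can help. An estimated score may be used in a randomized trial even though the allocation probability is known, and the first table shows a real fall in variability when the unbalanced covariates explain half the variance. This stands. A reader might infer that propensity adjustment at 42 infants adds noise as a rule. The protocol gives no prognostic strengths, so it cannot support that.

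A reader might also infer a large loss of power. With an assumed effect of 0.89 SD and two covariates explaining 25% of variance, weighting gave 78% power after a p < 0.05 screen and 74% after a 0.2 SD screen, against 88% for ANCOVA on those two covariates. But with no adjustment at all, power is about 80% (0.89/0.309 = 2.88, t test on 40 df). Most of the gap is thus the gain assumed for ANCOVA when the right covariates are known in advance. That ANCOVA's power falls to 83%, 81% and 78% as variance explained drops to 10%, 5% and 0%.

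Two further limits stand. The univariate tests and the propensity scores appear in separate sentences, so it is an inference that the tests decide which variables enter the score. The analysis is also labelled secondary in a single-center pilot. None of this supplies the missing covariate list, criterion or method, or repairs the interval.

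**Conclusion.** The point holds in a limited form. The secondary adjustment is unspecified and driven by observed imbalance. Under the assumed inputs it loses up to about a quarter of precision, measured by the true SD, when the selected covariates are not prognostic (ratios up to 1.21 as covariate, 1.26 with weighting). It gains when they are strongly prognostic (down to 0.76 and 0.86). In either case the reported SE is about 2-14% larger than that of baseline-only ANCOVA and does not track the true variability. The direction of the effect on precision in this trial cannot be known from the protocol.

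The primary comparison is untouched, and nothing here suggests that it is biased. The case for change is that a better-calibrated, pre-specified alternative costs almost nothing. The figures depend on the assumed number of candidate covariates, their independence, the correlation of 0.5 and the Stage I inputs.

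**What to change.** Replace the propensity-score sentence with one secondary model: ANCOVA of TBARS on treatment arm, baseline TBARS and the Stage I stratum. If the investigators believe that one or two other variables predict TBARS, name them before any unblinded data are seen, ahead of the interim analysis at 24 patients. Age and weight at surgery are possible candidates, but the protocol gives no evidence that they predict TBARS in infants under 30 days. Replace the baseline significance tests with a descriptive baseline table.

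The change is to wording only. It has two costs. A large chance imbalance in an unlisted variable would be described, not adjusted for. For example, with 15 candidates explaining 30% of variance, the baseline plus Stage I model had a type I error of 6.5% among trials in which a p < 0.05 screen would have flagged something, against 4.9% overall. Extra covariates that turn out not to be prognostic also cost a little precision, up to 3% in true SD for two of them.
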